2. OBJECTIVES AND ENDPOINTS

2.1. Objectives

2.1.1. Primary Objective

- Evaluate response rate [complete response (CR) + partial response (PR)] of nivolumab in combination with ramucirumab in subjects with previously-treated mesothelioma. Response assessment will be performed using modified RECIST 1.1 criteria as described by Byrne et al. [35].

2.1.2. Secondary Objectives

- Characterize adverse effects (AE) of nivolumab in combination with ramucirumab in subjects with previously-treated mesothelioma.
- Measure progression free survival (PFS) rate at 24 weeks with the combination of the anti PD-1 agent, nivolumab and the anti VEGFR2 antibody, ramucirumab in subjects with previously-treated mesothelioma.
- Measure overall survival (OS) at 2 years after treatment with nivolumab in combination with ramucirumab in subjects with previously-treated mesothelioma.

2.1.3. Correlative Objectives

- Correlate PD-L1 expression in tumor tissue (from biopsy before treatment) with best clinical response (modified RECIST 1.1 criteria) in subjects with previously-treated mesothelioma.
- Correlate change in PD-L1 expression in tumor tissue from before therapy (assessed within 14 days before treatment) to after 4 cycles (8 weeks) of therapy with best clinical response (modified RECIST 1.1 criteria) at the end of Cycle 4 (Week 8) in subjects with previously-treated mesothelioma.
- Correlate cytokine genes expressions in tumor tissue (such as IL-1, IL-2, IL-6, GM-CSF, IL-10, IL-12, T-bet, IRF1, IFN γ , CXCL1, CXCL9, CXCL10, CCL2 and 5) from before therapy (assessed within 14 days before treatment) to after 4 cycles (8 weeks) of therapy with best clinical response (modified RECIST 1.1 criteria) at the end of Cycle 4 (Week 8) in subjects with previously-treated mesothelioma.

- Correlate change in soluble PD-L1 level in plasma during therapy (assessed pre-dose Cycles 1 and 5 [(Days 1 and 57 of treatment period, respectively)]) relative to baseline with best clinical response (modified RECIST 1.1 criteria) at the end of Cycle 4 (Week 8) in subjects with previously-treated mesothelioma.
- Correlate change in number of CD8+, Granzyme B+ T cells in tumor tissue from before and during therapy (assessed within 14 days before treatment) to after 4 cycles (8 weeks) of therapy with best clinical response (modified RECIST 1.1 criteria) at the end of Cycle 4 (Week 8) in subjects with previously-treated mesothelioma.

3. ELIGIBILITY CRITERIA

Study entry is open to adults regardless of gender or ethnic background. While there will be every effort to seek out and include women and minorities, the subject population is expected to be no different than that of other advanced solid tumor cancer studies at each participating institution.

3.1. Inclusion Criteria

Subject must meet all of the following applicable inclusion criteria to participate in this study:

1. Male or female \geq 18 years of age at time of consent.
2. Histologically-confirmed malignant mesothelioma not amenable to curative surgery and who have received at least one pemetrexed-containing chemotherapy regimen.
3. Eastern Cooperative Oncology Group (ECOG) performance status of 0 or 1.
4. Adequate hepatic function within 28 days prior to study registration defined as meeting all of the following criteria:
 - total bilirubin < 1.5 mg/dL (25.65 μ mol/L) OR direct bilirubin \leq ULN for subjects with total bilirubin levels > 1.5 mg/dL (except subject with Gilbert's Syndrome, who can have total bilirubin < 3.0 mg/dL)
 - aspartate aminotransferase (AST) $\leq 3 \times$ ULN or $\leq 5 \times$ ULN for subjects with known hepatic metastases
 - alanine aminotransferase (ALT) $\leq 3 \times$ ULN or $\leq 5 \times$ ULN for subjects with known hepatic metastases
5. Adequate hematologic function within 28 days prior to study registration defined as meeting all of the following criteria:
 - hemoglobin ≥ 8 g/dL, subjects requiring transfusion will not be eligible to start study
 - and absolute neutrophil count (ANC) $\geq 1.5 \times 10^9/L$
 - and platelet count $\geq 100 \times 10^9/L$
6. Adequate renal function within 28 days prior to study registration by either of the following criteria:
 - serum creatinine ≤ 1.5 times the ULN, or creatinine clearance (measured via 24-hour urine collection) ≥ 40 mL/minute (that is, if serum creatinine is > 1.5 times the ULN, a 24-hour urine collection to calculate creatinine clearance must be performed)
 - subject's urinary protein is $\leq 1+$ on dipstick or routine urinalysis (UA; if urine dipstick or routine analysis is $\geq 2+$, a 24-hour urine collection for protein must demonstrate < 1000 mg of protein in 24 hours to allow participation in this protocol)

7. Adequate coagulation functioning within 28 days prior to study registration defined by either of the following criteria:
 - INR \leq 1.5, and a partial thromboplastin time (PTT) (PTT/aPTT) $< 1.5 \times$ ULN (unless receiving anticoagulant therapy)
 - Subjects on full-dose anticoagulation must be on a stable dose (minimum duration 14 days) of oral anticoagulant or low molecular weight heparin (LMWH). Patients receiving warfarin must be switched to low molecular weight heparin and have achieved stable coagulation profile prior to first dose of protocol therapy. For heparin and LMWH there should be no active bleeding (that is, no bleeding within 14 days prior to first dose of protocol therapy) or pathological condition present that carries a high risk of bleeding (for example, tumor involving major vessels or known varices).
8. Subjects must be willing to undergo a CT-guided biopsy (i.e., image-guided percutaneous lung biopsy) to obtain tumor tissue within 28 days before initiation of treatment and after 4 cycles (8 weeks) of treatment.
9. Women of childbearing potential (WOCP) must be willing to use birth control as outlined in Section 5.6.2.
10. Men who are not surgically or medically sterile must agree to use contraception as outlined in Section 5.6.2.
11. Measurable disease, defined as at least 1 tumor that fulfills the criteria for a target lesion according to modified RECIST 1.1 criteria, and obtained by imaging within 28 days prior to study registration.
12. Prior intracavity cytotoxic or sclerosing agents (including bleomycin) is acceptable.
13. Radiation therapy must be completed $>$ 28 days before study registration, and the measurable disease must be outside of the radiation port.
14. Pemetrexed-containing chemotherapy must be completed $>$ 28 days before study registration.
15. Must provide written informed consent and HIPAA authorization approved by an Institutional Review Board (IRB). NOTE: HIPAA authorization may be included in the informed consent or obtained separately.
16. All previous toxicity resolved to Grade 1 or less.

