1.2. Study Rationale

The programmed death ligand 1 (PD-L1) [16] and VEGFR2 [34] are highly-expressed on mesothelioma cells, and are therefore attractive options for this cancer. We chose to study the combination of ramucirumab with nivolumab because of the potential efficacy of these two agents in mesothelioma and because of the potential synergistic activity between them [30]. As previously discussed, immunotherapies such as anti-PD-1 inhibitors must contend with a hostile, immunosuppressive tumor microenvironment due to angiogenesis that results in hypoxia. This hypoxia decreases the ability of antibodies to infiltrate the tumor. We hypothesize that the normalization of tumor vasculature (by reducing the area of the tumor that is hypoxic) with an anti-VEGF strategy (i.e., ramucirumab) used in synergy with a PD-1 inhibitor will facilitate the infiltration of T-lymphocytes into tumor parenchyma. We will conduct a phase II study based on this premise using nivolumab and ramucirumab as second-line therapy in patients with malignant mesothelioma who have failed standard doublet platinum and anti-folate therapy.

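### Eligibility requires that pemetrexed was received, not that it failed, so patients still in disease control can enter and favour the 24-week PFS rate and 2-year OS in a trial with no control arm

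*Combined protocol and SAP*

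**What the plan says.** **Who may enter.** Section 3.1, item 2 reads: "Histologically-confirmed malignant mesothelioma not amenable to curative surgery and who have received at least one pemetrexed-containing chemotherapy regimen". The Synopsis (key eligibility criteria) and Section 5.1 use the same condition. Nothing in Sections 3.1 or 3.2 asks for progression or recurrence.

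**Who the trial is for.** Section 1.2 proposes the combination as second-line therapy for "patients with malignant mesothelioma who have failed standard doublet platinum and anti-folate therapy". Section 1.1 also describes the unmet need as that of patients whose pemetrexed-containing treatment has failed.

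**Prior-therapy rules.**
- Item 14: "Pemetrexed-containing chemotherapy must be completed" more than 28 days before registration.
- Item 13: radiation must have ended more than 28 days before registration, and "the measurable disease must be outside of the radiation port".
- Exclusion 29: no investigational agent within 28 days before registration.
- Exclusion 27: no prior checkpoint therapy at any time.
- Section 5.5.2: no other systemic anticancer therapy during screening and treatment.
- Item 12: "Prior intracavity cytotoxic or sclerosing agents (including bleomycin) is acceptable", with no interval given.

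**Baseline and response.** Under item 11, measurable disease must be "obtained by imaging within 28 days prior to study registration". Section 8.4 also limits the baseline scan to the 4 weeks before treatment starts. Sections 8.1.2 and 8.5.1 require a partial response to be a fall of 30% or more from that baseline, confirmed at least 4 weeks later. Section 8.1.4 counts an unconfirmed response as stable disease.

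**The concern.** The criterion that sites will apply admits a wider population than the rationale describes. A patient who has just finished first-line pemetrexed in response or stable disease meets item 2 as soon as item 14 is satisfied.

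That patient's expected course is better than that of a patient whose disease has already progressed. A randomised control arm would share the advantage and cancel it. This trial has one arm, so the advantage goes into the 24-week PFS rate and 2-year OS of Section 2.1.2 and is credited to nivolumab plus ramucirumab. The result would also answer a different question from whether the combination is active once pemetrexed has failed.

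A second route is late shrinkage from earlier treatment counted as response. This matters because Section 12.3 judges the response rate against a fixed 20%. The documents describe the patients behind that 20% only as having malignant mesothelioma, so whether the comparison is like for like cannot be checked.

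**Working it through.** **1. The plan's own figure.** Section 12.3 uses p0 = 0.20, p1 = 0.40, one-sided alpha 0.05 and 80% power, and gives 33 evaluable.
- Normal approximation with null and alternative variances: 28.6, so 29.
- With continuity correction: 33.4, so 34.
- Exact binomial: the smallest n with alpha at most 0.05 and power at least 0.80 is 35 (12 or more responses; alpha 0.034, power 0.805).
- Inflation: 33/0.95 = 34.7, so 35, as stated.

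The stated 33 lies within 2 of these last two results. Nothing below changes the sample size.

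**2. Effect on the 24-week PFS rate.** Section 1.1 gives first-line median PFS of 7.5 months (cisplatin-pemetrexed) and 9.6 months (with bevacizumab). Assume exponential PFS and no effect of trial drug. The exponential has no memory, so the chance of a further 24 weeks without progression does not depend on when the patient enters.
- 24 weeks = 168/30.44 = 5.52 months.
- 2^(−5.52/7.5) = 0.60.
- 2^(−5.52/9.6) = 0.67.

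Let f be the share of subjects enrolled without progression, and q the 24-week rate in progressed patients. The documents give neither; take q = 0.30 to 0.40 as an assumption. The observed rate is shifted by f × (0.60 or 0.67 − q). For f = 0.10 (3.5 of 35 subjects):

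| q | 7.5-month median | 9.6-month median |
|---|---|---|
| 0.40 | 2.0 points | 2.7 points |
| 0.30 | 3.0 points | 3.7 points |

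For scale, the approximate 95% half-width for a rate of 35% in 35 subjects is 1.96 × √(0.35 × 0.65/35) = 0.158, or about 16 points. The shift at f = 0.10 is well inside sampling error, but it is a bias in one direction and grows in proportion to f.

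For 2-year OS the direction is the same, but the documents give no figures from which to size it.

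**3. Timing of the baseline scan.** Call registration day 0. Item 14 puts the end of pemetrexed at day −29 or earlier, and item 11 puts the scan at day −28 or later. The scan therefore always follows the last pemetrexed dose, by at least 1 day. If treatment starts t days after registration, Section 8.4 moves the earliest scan to day −28 + t, and the gap is at least 1 + t days. The 1-day gap therefore needs the shortest washout, the earliest scan and treatment on the day of registration together. Shrinkage before the scan cannot count as response; shrinkage after it can.

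**4. Response rate, illustration only.** Suppose a share c of subjects respond solely because of earlier treatment. The effective null rate is 0.20 + 0.80c, so c = 2.5% gives 0.22 and c = 5% gives 0.24. The documents give no value for c and state no success cut-off. Exact binomial chance of meeting three possible cut-offs:

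| Cut-off | rate 0.20 | rate 0.22 | rate 0.24 |
|---|---|---|---|
| 11 or more of 33 | 0.051 | 0.091 | 0.147 |
| 12 or more of 33 | 0.022 | 0.043 | 0.077 |
| 12 or more of 35 | 0.034 | 0.066 | 0.112 |

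**The case against.** **The eligibility text matches the stated objective.** The objectives in Section 2.1 and the design text in Section 12.1 speak of previously treated disease, and Section 5.1 states the primary objective in the terms of item 2. Only the background and rationale speak of failure. This stands as far as it goes: the conflict lies between the rationale and the rest of the protocol. It does not remove the effect on PFS and OS.

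**Response is well protected.** A carried-over response would need a further 30% fall from a post-chemotherapy baseline, seen at the first on-study scan at week 8 or later and confirmed at least 4 weeks after that. Patients whose tumours have already shrunk may also have less room for another 30% fall, so admitting them could lower the response rate. This largely stands. Confirmation shows that shrinkage persists but not which treatment caused it, so carry-over is narrowed without being excluded.

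**PFS and OS are descriptive.** Section 12.5 gives estimates with confidence intervals and no test or threshold. True, but these estimates are how readers will place the combination against other treatment.

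**The number of such patients is unknown.** Entry also requires measurable disease and willingness to undergo two biopsies. The first-line medians describe first-line patients in general and cannot supply f.

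**What a reader might infer about washout.** It is tempting to conclude that only the pemetrexed regimen has a washout. The documents do not support that: item 13 covers radiation, exclusion 29 covers investigational agents, exclusion 27 bars prior checkpoint therapy, and Section 5.5.2 bars other systemic therapy from screening onward. The remaining gap is narrow: no fixed interval is stated for other non-investigational systemic therapy given before screening, or for intracavity cytotoxics.

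**Conclusion.** The point holds, with moderate confidence. Item 2 and Section 1.2 describe different populations, and no criterion keeps out patients whose disease is still controlled after pemetrexed.

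The main consequence is for 24-week PFS and 2-year OS. Each 10% of enrolment without progression adds about 2 to 4 points to the 24-week PFS rate. That rests on exponential PFS with the Section 1.1 medians, no effect of trial drug in these patients, and an assumed 30% to 40% rate in progressed patients. If the risk of progression rises once chemotherapy stops, the shift is smaller.

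A reader might go further and infer that the type I error of the primary test rises to 9% to 15%. The documents do not support that. The range needs an assumed response rate of 22% to 24% without true activity, together with a cut-off of 11 of 33, which the plan does not state and which already slightly exceeds 0.05 at the null. With 12 of 33 the same assumption gives 4.3% to 7.7%. The size of any carry-over into response is unknown and its net direction is not certain.

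**What to change.** 1. Reconcile Section 1.2 with Section 3.1 item 2, the Synopsis and Section 5.1. Amend item 2 to require documented progression or recurrence during or after prior pemetrexed-containing therapy, which is the population the rationale already states.
2. For subjects already enrolled, record progression status at entry and the date of last prior therapy. Report the response rate, PFS and OS with and without subjects who had not progressed. Section 7, footnote 1 already collects prior treatments, so this is mainly one added data item.
3. Have the sponsor reconcile items 12 to 14, exclusion 29 and Section 5.5.2, so that the protocol says plainly what applies to other prior systemic therapy and to intracavity agents. Item 12 expressly permits the latter. Whether an interval is needed, and what it should be, is a clinical decision for the sponsor.

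The cost is one eligibility amendment, one data item and slightly slower accrual. No procedures are added and the sample size does not change.

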KEY ELIGIBILITY CRITERIA (See Section 3 for full eligibility criteria)	
 Male or female \geq 18 years of age at time of consent. Histologically-confirmed malignant mesothelioma not amenable to curative surgery and who have received at least one pemetrexed-containing chemotherapy regimen. Has an Eastern Cooperative Oncology Group (ECOG) performance status of 0 or 1. Adequate hepatic function within 28 days prior to study registration defined as meeting all of the following criteria: 
 total bilirubin $<$ 1.5 mg/dL (25.65 μmol/L) OR direct bilirubin \leq ULN for subjects with total bilirubin levels $>$ 1.5 mg/dL (except subject with Gilbert's Syndrome, who can have total bilirubin $<$ 3.0 mg/dl) aspartate aminotransferase (AST) \leq 3 \times ULN or \leq 5 \times ULN for subjects with known hepatic metastases alanine aminotransferase (ALT) \leq 3 \times ULN or \leq 5 \times ULN for subjects with known hepatic metastases Adequate hematologic function within 28 days prior to study registration defined as meeting all of the following criteria: 
 hemoglobin \geq 8 g/dL, subjects requiring transfusion will not be eligible to start study and absolute neutrophil count (ANC) \geq 1.5 \times 10⁹/L and platelet count \geq 100 \times 10⁹/L Adequate renal function within 28 days prior to study treatment by either of the following criteria: 
 Serum creatinine \leq 1.5 the ULN if serum creatinine $>$ 1.5 the ULN, estimated glomerular filtration rate (GFR) \geq 40 mL/min Adequate coagulation functioning within 28 days prior to study registration defined by either of the following criteria: 
 INR \leq 1.5, and a partial thromboplastin time (PTT) (PTT/aPTT) $<$ 1.5 \times ULN (unless receiving anticoagulant therapy) Subjects on full-dose anticoagulant must be on a stable dose (minimum duration 14 days) of oral anticoagulant or low molecular weight heparin (LMWH). Patients receiving warfarin must be switched to low molecular weight heparin and have achieved stable coagulation profile prior to first dose of protocol therapy. See section 3.1 for additional information.

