7 STUDY CALENDAR & EVALUATIONS

Study Day [Cycle = 14 days]	Screen	Cycle 1	Cycle 2 +	Safety Follow up ¹⁴	Safety Follow up ¹⁴	Long Term Follow Up ¹⁵
	-28 days	Day 1 (± 3)	Day 1 (± 3)	30 days (±7)	90 days (±7)	Q 3 months (±14 days)
REQUIRED ASSESSMENTS						
Informed Consent/HIPAA auth.	X					
Medical History ¹	X					
Physical Exam	X	X	X	X		
Vital Signs including ECOG PS ²	X	X	X	X		
AE Assessment and Con Meds	X	X	X	X	X	
LABORATORY ASSESSMENTS						
Blood Chemistries ³	X	X ¹³	X	X		
Thyroid Function Testing ⁴	X	X ¹³	X	X		
PT/INR and aPTT	X	X ¹³	X	X		
Platelets, ANC & Hgb	X	X ¹³	X	X		
Urinalysis	-7d ⁵	X ¹³	X			
Pregnancy Test for WOCP ⁶	X	-24h	X ⁶			
DISEASE ASSESSMENT						
CT or MRI chest, abdomen/pelvis ⁷	X		X			X
CT or MRI Brain, if indicated ⁷	[X]					
TREATMENT						
Nivolumab		X	X			
Ramucirumab		X	X			
CORRELATIVE STUDIES						
CT-guided biopsy ⁸	X		X ⁸			
Whole Blood for Somatic Baseline ⁹		X				
Serum for soluble PD-L1 analysis ⁹		X	C5D1			
BANKING SAMPLES						
Whole Blood ¹⁰ - Optional		X				
Serum and Plasma ¹¹ - Optional		X		X		
Unstained Slides ¹² - Optional		X	X ¹²			
FOLLOW UP						
Survival status, additional cancer therapy						X

Footnotes:

1. Medical history to include demographics, prior treatments, radiation and surgical history. Other information obtained during the medical history includes: Smoking history to include: amount, frequency, start and stop dates of cigarette, cigar and pipe usage. A question about how the patient heard about the study. Prior genetic or biomarker testing results will be required if available.
2. Vital signs to include BP, HR, weight, height (screening) only. In addition, ECOG performance status should be obtained.
3. Blood Chemistries to include: sodium, potassium, blood urea nitrogen (BUN), serum creatinine (or GFR; see 3.1.7), calcium, albumin, ALT, AST, bilirubin, alkaline phosphatase (ALK), total protein, glucose.
4. Thyroid studies will be obtained every 3 cycles (about 6 weeks) starting with Cycle 4 (\pm 7 day window). The type of testing performed (TSH, T3 free vs direct, or T4 free vs direct) should be per local standards.
5. Within 1 week of study registration. If urine dipstick or routine analysis is $\geq 2+$, a 24-hour urine collection for protein must demonstrate < 1000 mg of protein in 24 hours to allow participation in this protocol.

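### Section 3.1 item 6 joins the filtration and urine-protein limits by 'either', so read literally it sets no binding creatinine or clearance limit and contradicts its own protein condition

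*Combined protocol and SAP*

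**What the plan says.** Section 3.1 opens with "Subject must meet all of the following applicable inclusion criteria to participate in this study". That sentence governs the numbered items; it does not say how bullets inside an item combine.

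Item 6 then requires "Adequate renal function within 28 days prior to study registration by either of the following criteria". Its two bullets are:

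- **Filtration.** Serum creatinine at most 1.5 times ULN, or "creatinine clearance (measured via 24-hour urine collection") of at least 40 mL/min. When creatinine is above the limit, "a 24-hour urine collection to calculate creatinine clearance must be performed".
- **Urine protein.** At most 1+ on dipstick or urinalysis. At 2+ or more, "a 24-hour urine collection for protein must demonstrate < 1000 mg of protein in 24 hours to allow participation in this protocol".

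Items 4 (hepatic) and 5 (hematologic), directly above, ask for all of their bullets to be met.

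The synopsis also uses 'either' in its renal criterion, but there the word joins creatinine to an "estimated glomerular filtration rate (GFR") of at least 40 mL/min. It has no protein bullet, and it counts its 28 days back from study treatment, not registration. Its heading sends the reader to Section 3 for the full criteria.

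In the Section 7 calendar, footnote 5 repeats the urine-protein condition on its own, with a window of one week before registration. Footnote 3 lists "serum creatinine (or GFR; see 3.1.7").

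**The concern.** An eligibility item should give every site the same answer for the same subject. Here the connector makes two unlike limits into alternatives, while the bullets are phrased as requirements. Item 6 is the only place in Section 3 with a limit on filtration, so if passing the protein bullet is enough, creatinine has no upper bound at entry.

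The protocol itself treats both quantities as relevant to safety. Section 10.1.5 lists proteinuria and nephrotic syndrome among the important identified risks of ramucirumab. Section 10.3 lists renal failure as an overlapping toxicity of the two drugs. In a single-arm study of 35 subjects, adverse events are described without a control group. A subject who enters with impaired renal function under one site's reading and would be refused under another's makes later renal events harder to attribute.

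**Working it through.** No arithmetic applies to the main point, and the plan gives no figure to reproduce. The check is to take the four possible results and read each against the three places that state the rule. F is the filtration bullet (creatinine or clearance); P is the urine-protein bullet.

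| F | P | Item 6 lead-in ('either') | Item 6 if both bullets were required | Other text |
|---|---|---|---|---|
| pass | pass | meets | meets | no conflict |
| fail | pass | **meets** | does not meet | Synopsis: does not meet (creatinine and GFR both failed) |
| pass | fail | **meets** | does not meet | Second bullet and calendar footnote 5: no participation |
| fail | fail | does not meet | does not meet | no conflict |

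**Can 'either' simply mean creatinine or clearance?** In the synopsis it does. In Section 3.1 that choice already sits inside the first bullet, joined by its own 'or'. The lead-in is left to join filtration to protein.

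**F fails, P passes.** No other inclusion item and no exclusion criterion in Section 3.2 sets a creatinine or clearance limit. Only the synopsis disagrees, and it names Section 3 as the full text. The literal result therefore stands in the controlling section. For this check I read the synopsis GFR limit and the Section 3.1 clearance limit as failed together; they are different measurements and could disagree.

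**F passes, P fails.** The lead-in says the renal item is met; the second bullet and footnote 5 say the subject may not take part. This is a contradiction, and a careful reader would follow the bar.

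**Other differences between the three places:**

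| Feature | Synopsis | Section 3.1 item 6 | Section 7 calendar |
|---|---|---|---|
| Measure when creatinine is high | estimated GFR | 24-hour measured clearance | GFR named in footnote 3 |
| Window counted back from | study treatment | registration | registration (footnote 5, urinalysis) |
| Urinalysis window | no protein criterion | 28 days | 1 week |
| Cross-reference | Section 3 | – | 3.1.7, which is coagulation |

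A urinalysis 8 to 28 days old satisfies item 6 but not footnote 5, a gap of 28 − 7 = 21 days. The reference in footnote 3 fails twice: renal function is item 6, and item 6 does not mention GFR.

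**The case against.** The best defence is that a site reading the protocol as a whole would not admit a subject with failed filtration. The first bullet demands a 24-hour collection when creatinine is high, which would be pointless if a clean dipstick were enough. The synopsis confines 'either' to creatinine versus GFR. Exclusion 22 lets the investigator refuse anyone whose safety might be jeopardized. All of this is fair as evidence of intent. But the first bullet requires only that the test be performed and does not state, as the second does, that its result is a condition of participation. The synopsis yields to Section 3. Exclusion 22 is a judgement, not a limit. Intent has to be inferred where an entry criterion should state it.

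A reader might go further and infer that a subject with heavy proteinuria and normal creatinine is eligible, and would then meet the Table 2 hold level of 2 g/24 hours at once. The documents do not support that. The second bullet and footnote 5 both bar such a subject, and Table 2 is written for drug-related adverse events, which proteinuria already present at screening is not obviously.

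Nor is the missing protein limit in the synopsis an error in itself: a list of key criteria that refers to Section 3 may be abridged. The mismatch between estimated GFR and measured clearance is different, because there the synopsis states a different rule.

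**Conclusion.** The item is wrong as written and should be corrected. In one of the four combinations (filtration failed, protein acceptable) the controlling text admits a subject whom the synopsis would refuse. In a second (filtration acceptable, protein failed) the lead-in contradicts the bullet beneath it and the calendar. The other two are unaffected.

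That the protein limit is a condition of entry is stated outright. That the filtration limit is also meant to be one is an inference from the synopsis and from the structure of the first bullet; it is plausible but not stated. How many subjects would be affected cannot be worked out, because the documents give no distribution of screening creatinine, clearance or urine protein. The sample size, one-sided alpha and power do not depend on this item. The differences in measure, reference date and urinalysis window are real but secondary, and the 3.1.7 reference is an editorial slip.

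**What to change.** - Reconcile the item 6 connector with the wording of its bullets and with calendar footnote 5, so that it is explicit whether both limits must be met.
- Align the synopsis, item 6 and the calendar on the renal measure (estimated GFR or 24-hour clearance), the date from which the window is counted, and the urinalysis window.
- Correct the 3.1.7 reference in calendar footnote 3.

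Which clinical rule applies is for the sponsor to decide; the request is that the three places state the same one. The cost is wording in an amendment and possibly a few more screen failures. No statistical section needs to change.
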